Eligible patients are randomly allocated in a 1:1 ratio to the ‘higher PEEP’ or ‘lower PEEP’ strategy. The allocation sequence is computer–generated by an independent investigator using permuted blocks of random size of four, six, and eight patients, and stratified per center. Randomization is performed by local investigators patient–by–patient employing a dedicated, password protected, SSL–encrypted website.

At each site, at least two investigators are involved with the study. One local investigator randomizes the patients immediately before surgery, and is

responsible for the trial intervention and data collection. A second local investigator remains blinded to the assigned treatment, and is responsible for postoperative data collection.

Outcomes

The primary study outcome is a collapsed composite of PPC developing within the first five postoperative days. This endpoint follows the European Perioperative Clinical Outcome (EPCO) definition and has been used before in several clinical trials.²⁻⁴ A patient that develops one or more PPCs is considered as meeting the primary outcome. The components of the composite outcome of PPC have been defined and described elsewhere,¹ and include: 1) aspiration pneumonitis; 2) moderate respiratory failure; 3) severe respiratory failure; 4) acute respiratory distress syndrome (ARDS); 5) pulmonary infection; 6) atelectasis; 7) cardiopulmonary edema; 8) pleural effusion; 9) pneumothorax on the non-surgical lung; 10) pulmonary infiltrates; 11) prolonged air leakage; 12) purulent pleuritic; 13) pulmonary embolism; and 14) lung hemorrhage. The selected PPC can sensibly be merged as they share common pathophysiological mechanisms and have plausibility to be affected in the same direction by the intervention tested in this study.

Secondary outcomes include: 1) extended PPC, including bronchospasm or mild respiratory failure; 2) severe PPC, as defined in a recent published clinical trial⁵ (composite of severe respiratory failure, pneumothorax, ARDS, pulmonary infection, prolonged air leakage, purulent pleuritis, new requirement of non-invasive or invasive ventilation due to respiratory failure and/or atelectasis); 3) a composite outcome of intraoperative complications, including use of continuous positive airway pressure for the non-ventilated lung, use of inhaled nitric

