models with binomial distribution and an identity link for binary variables (reported as difference in percentages). Plots comparing ventilatory variables and vital signs among the groups during the first three hours of surgery and in the last hour will be drawn (presenting the data as mean and 95% confidence interval in each time point).

Other daily characteristics

Daily variables will be reported according to the description in **Proposed Inserts**. Absolute differences between groups will be calculated using median regression for continuous variables (reported as median difference) and generalized linear models with binomial distribution and an identity link for binary variables (reported as difference in percentages). Plots comparing daily variables among the groups will be constructed (presenting the data as mean and 95% confidence interval in each time point).

Primary outcome

The effect of 'higher PEEP' compared to 'lower PEEP' on the incidence of PPC will be assessed using a mixed-effect generalized linear model with binomial distribution and identity link, with sites included as random effects to account for the clustering effect and reported as absolute difference with a two-sided 95% confidence interval. Results will be presented in a table of outcomes (**Proposed Inserts**).

Secondary outcomes

For binary outcomes, the effect of 'higher PEEP' compared to 'lower PEEP' will be assessed using a mixed-effect generalized linear model with binomial distribution and identity link, with sites included as random effects to account for the clustering effect and reported as absolute difference with a two-sided 95%

confidence interval. For continuous outcomes, the comparison will be made using a mixed-effect median regression with sites also including as clustering effect, and reported as median difference with a two-sided 95% confidence interval. 90-day mortality will be assessed using Kaplan–Meier curves, and hazard ratios with 95% confidence intervals will be calculated with (shared-frailty) Cox proportional hazard models without adjustment for covariates and including sites as frailty. The proportional hazard assumptions will be tested using scaled Schoenfeld residuals and alternative parametric survival models will be used if the proportionality assumption is not sustained. In addition, a Holm–Bonferroni correction to control the family-wide error rate to the p values for all secondary outcomes will be done and presented in a Table.

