Per-protocol analysis

The per-protocol population will consist of patients truly ventilated according to the protocol. Thus, patients will be excluded from this population if receiving PEEP < 10 cm H₂O in the ‘higher PEEP’ group or PEEP > 5 cm H₂O and FiO₂ < 1.0 in the ‘lower PEEP’ group, unless rescue for hypoxemia or hypercapnia required adjustments of PEEP and FiO₂ as defined by the protocol.

Subgroup analysis

Treatment effects on incidence of PPC will be analyzed according to the following predefined subgroups: 1) type of surgery (non-thoracoscopic versus thoracoscopic); 2) positioning (lateral decubitus versus supine position); 3) baseline SpO₂ < 96% versus SpO₂ ≥ 96%; 4) chronic obstructive pulmonary disease (COPD) versus non-COPD; 5) body mass index < 30 kg/m² versus ≥ 30 kg/m²; and 6) duration of one-lung ventilation < 120 versus ≥ 120 minutes. Analyses of heterogeneity of effects across subgroups will be performed with the

use of treatment-by-subgroup term added to the primary model and will be presented in a forest plot.

Other exploratory analyses

Given that the primary outcome of the present study is a collapsed composite, the choice of the statistical method is an important part of designing since various methods provide different power, depending on the situation. In addition to the standard analysis described above, the following analyses will be performed:

- Count analysis: the number of positive component events (i.e., 'count') across the composite will be assessed. The groups will be compared on the count using a Wilcoxon rank sum test, and the odds ratio with the 95% confidence interval will be assessed with a cumulative logistic regression model;
- Individual component analysis: the effect of the intervention in each component will be analyzed estimating the risk ratio and confidence intervals with Wald's likelihood ratio approximation test using a Bonferroni correction for multiple comparisons. The 99.6% Bonferroni-corrected confidence intervals will be reported ($1 - 0.05/14 = 0.996$);
- Common effect test: A multivariate (i.e., multiple outcomes per subject) generalized estimating equations (GEE) model will be used to estimate a common effect odds ratio across the components;

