Figure 2	Postoperative Pulmonary Complications in Prespecified Subgroups A forest plot showing the absolute difference and two-sided 95% confidence intervals with p value for interaction calculated via a test for treatment-by-subgroup interaction in the regression model. A solid line of reference in the number 1 and a dashed line of reference in the overall effect will be shown.
Online Supplement	
eTable 1	Rate of Missing Data A table showing the rate of missing data.
eTable 2	Additional Baseline Characteristics A table showing additional baseline characteristics.
eTable 3	Additional Intraoperative Characteristics A table showing additional intraoperative characteristics.
eTable 4	Intraoperative Fluid and Drug Therapy A table reporting intraoperative fluid and drug therapy each arm.
eTable 5	Protocol Deviations A table describing protocol deviations.
eTable 6	Daily Assessment of Included Patients A table describing daily assessment of patients.
eTable 7	Additional Daily Assessment of Included Patients A table describing daily assessment of patients.
eTable 8	Daily Signs and Laboratory of Included Patients A table describing daily assessment of patients.
eTable 9	Day 1 Fluid and Drug Therapy A table reporting day 1 fluid and drug therapy each arm.
eTable 10	Multiplicity adjustment for secondary outcome analyses A table showing the observed p values for all the secondary outcomes and ordered from the lower until the higher and the corrected p values using a Holm-Bonferroni correction
eTable 11	Sensitivity Analyses for the Primary Outcome A table showing the proposed sensitivity analyses for the primary outcome (count analysis, common effect test, average relative effect test and heterogeneity of treatment effect)
eFigure 1	Tidal Volume, PEEP, Peak Pressure, Plateau Pressure, Driving Pressure and FiO ₂ During Surgery Line graph reporting the mean and 95% confidence interval of the variables at induction, final positioning with two lung ventilation, 10 minutes of one lung ventilation and at the end of surgery by treatment group.
eFigure 2	VAS Dyspnea, VAS Thoracic Pain, VAS Coughing Pain, Respiratory Rate, SpO ₂ and Mean Arterial Pressure During the First Five Days of Follow-Up Line graph reporting the mean and 95% confidence interval of the variables in the first five days of follow-up by treatment group.

eFigure 3

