Time-to-event analyses for PPC	Kaplan–Meier curves will be used to report time to postoperative pulmonary complications, and hazard ratios with a 95% confidence interval will be calculated with Cox proportional hazard models without adjustment for covariates.	No time-to-event analysis planned to be performed for PPC.
Time-to-event analyses for 90-day mortality	Hazard ratios with 95% confidence intervals will be calculated with Cox proportional hazard models without adjustment for covariates and including sites as frailty.	Hazard ratios with 95% confidence intervals will be calculated with (shared-frailty) Cox proportional hazard models without adjustment for covariates and including sites as frailty.
Subgroup analysis (definition)	---	Added two additional subgroups: body mass index and duration of one-lung ventilation.
Subgroup analysis (method)	The effects on subgroups will be evaluated according to the interaction effects between each subgroup and the study arms by generalized linear models and presented in a forest plot.	Analyses of heterogeneity of effects across subgroups will be performed with the use of treatment-by-subgroup term added to the primary model and will be presented in a forest plot.

LIST OF PROPOSED INSERTS

Table 1 – Baseline Characteristics of the Included Patients

	Higher PEEP (n =)	Lower PEEP (n =)
Age, years		
Age ≥ 65 years – no. (%)		
Female gender – no. (%)		
Body mass index, kg/m ²		
Body mass index ≥ 30 kg/m ²		
ARISCAT score		
ARISCAT ≥ 45 – no. (%)		
ASA physical status– no. (%)		
1		
2		
3		
4		
Priority of surgery – no. (%)		
Elective		
Urgent		
Emergency		
Surgical procedure – no. (%)		
Thoracoscopic		
Open		
Converted from thoracoscopic to open		
Cumulated ambulation score		
Co-existing disorders – no. (%)		
Hypertension		
Heart failure		
Coronary artery disease		
Diabetes		
Obstructive sleep apnea		
Chronic obstructive pulmonary disease		
Use of noninvasive ventilation		
Active cancer		
Respiratory infection within last month		
Smoking status		
Never		
Former (cessation > 3 months)		
Current		
Alcohol (> 2 drinks/day)		
Preoperative signs		
SpO ₂ , %		
Respiratory rate, breaths/min		
Heart rate, beats per minute		
Mean arterial blood pressure, mmHg		

Data are median (quartile 25th - quartile 75th) or N / total (%).

Abbreviations: PEEP is positive end-expiratory pressure; ARISCAT is The Assess Respiratory Risk in Surgical Patients in Catalonia; ASA is American Society of Anesthesiology; SpO₂ is pulse oximetry.

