Table 2 – Ventilation and Intraoperative Characteristics

	Higher PEEP (n =)	Lower PEEP (n =)	Absolute Difference (95% CI)	p value
Recruitment maneuver – no. (%)				
Number of recruitment maneuvers				
Tidal volume, mL/kg PBW				
Induction				
Final position with two lung ventilation				
10 minutes after one lung ventilation				
End of surgery, supine, two lung ventilation				
PEEP, cmH ₂ O				
Induction				
Final position with two lung ventilation				
10 minutes after one lung ventilation				
End of surgery, supine, two lung ventilation				
Peak pressure, cmH ₂ O				
Induction				
Final position with two lung ventilation				
10 minutes after one lung ventilation				
End of surgery, supine, two lung ventilation				
Plateau pressure, cmH ₂ O				
Induction				
Final position with two lung ventilation				
10 minutes after one lung ventilation				
End of surgery, supine, two lung ventilation				
Driving pressure, cmH ₂ O				
Induction				
Final position with two lung ventilation				
10 minutes after one lung ventilation				
End of surgery, supine, two lung ventilation				
Respiratory rate, breaths/min				
Induction				
Final position with two lung ventilation				
10 minutes after one lung ventilation				
End of surgery, supine, two lung ventilation				
FiO ₂				
Induction				
Final position with two lung ventilation				
10 minutes after one lung ventilation				
End of surgery, supine, two lung ventilation				
SpO ₂ , %				
Induction				
Final position with two lung ventilation				
10 minutes after one lung ventilation				
End of surgery, supine, two lung ventilation				

Table 2 – Ventilation and Intraoperative Characteristics

	Higher PEEP (n =)	Lower PEEP (n =)	Absolute Difference (95% CI)	p value
etCO ₂ , mmHg				
Induction				
Final position with two lung ventilation				
10 minutes after one lung ventilation				
End of surgery, supine, two lung ventilation				
Mean arterial pressure, mmHg				
Induction				
Final position with two lung ventilation				
10 minutes after one lung ventilation				
End of surgery, supine, two lung ventilation				
Duration of anesthesia, min				
Duration of one lung ventilation, min				
Duration of two lung ventilation, min				
Duration of surgery, min				
Duration of surgery ≥ 180 min – no. (%)				
Fluids				
Total intake, mL				
Fluid balance, mL				

Data are median (quartile 25th - quartile 75th) or N / total (%).

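### Subgroup 6 splits on one-lung ventilation duration, which is known only after randomisation, and the Figure 2 forest plot of absolute differences puts its solid reference line at 1 instead of 0

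*SAP*

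**What the plan says.** **Duration subgroup.** The Subgroup analysis section gives six predefined subgroups for the primary outcome. The sixth is "duration of one-lung ventilation < 120 versus ≥ 120 minutes". The third, by contrast, is tied to a time before treatment: "baseline SpO₂ < 96% versus SpO₂ ≥ 96". On timing, Randomization and blinding states: "One local investigator randomizes the patients immediately before surgery". The table of modifications from the original plan records the change: "Added two additional subgroups: body mass index and duration of one-lung ventilation". Among the table shells, "Duration of one lung ventilation, min" appears in proposed Table 2 (Ventilation and Intraoperative Characteristics), which has columns for the difference between arms and a p value. It is not in the baseline shells (Table 1 and eTable 2).

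**Reference line.** The Primary outcome section specifies an identity-link model, "reported as absolute difference with a two-sided 95% confidence interval". Subgroup effects come from that model with an interaction term added. Table 3 of the SAP describes main-paper Figure 2 as a "forest plot showing the absolute difference and two-sided 95% confidence intervals", and then says: "A solid line of reference in the number 1 and a dashed line of reference in the overall effect will be shown".

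**The concern.** A subgroup analysis compares randomised arms within each stratum only if stratum membership could not have been influenced by allocation. One-lung ventilation duration accrues after allocation. If one strategy lengthens or shortens it, some patients in that arm cross the 120-minute cut who would not have crossed it in the other arm. Longer cases may also be the more complex ones, with a higher risk of pulmonary complications. Each stratum estimate would then mix treatment effect with case-mix, yet it would sit in the forest plot beside true baseline subgroups with nothing to warn the reader.

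The reference line is a plain contradiction. For a difference, no effect is 0; the value 1 is the null only for a ratio. If the figure is drawn as described, a reader who takes the solid line as no effect will misjudge which intervals include it.

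**Working it through.** **1. Inputs from the SAP.** Incidence is 23% with lower PEEP and 17.25% with higher PEEP, so the difference is 17.25 − 23 = −5.75 percentage points (pp) and the risk ratio is 17.25/23 = 0.75. Table 2 gives N = 2259 before dropout; 2259/0.95 = 2378, which reproduces the stated total. None of these figures is in dispute.

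**2. What a line at 1 means.** Equal risks give 23% − 23% = 0. On a proportion axis, 1 is +100 pp. On a percentage-point axis, 1 is +1 pp, for example 24% against 23%, which is harm.

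**3. Size of the displacement on a percentage-point axis.** For a subgroup holding half the patients, n per arm = 2259/4 = 564.75.

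- SE = √[(0.23×0.77 + 0.1725×0.8275)/564.75] = √(0.31984/564.75) = 2.38 pp.
- 95% half-width = 1.96 × 2.38 = 4.66 pp, and 1/4.66 = 21%.
- With 20% of patients the half-width is 7.38 pp and the ratio 14%; with 80% they are 3.69 pp and 27%.

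**4. How often a row is misread.** Take the difference as higher minus lower PEEP, with true value d. An interval lies wholly below a line at L with probability Φ((L − 4.66 − d)/2.38).

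| True difference | Wholly below 0 | Wholly below +1 | Relation to +1 differs from relation to 0 |
|---|---|---|---|
| −5.75 pp | Φ(0.456) = 68% | Φ(0.876) = 81% | 13.4% |
| 0 | Φ(−1.96) = 2.5% | Φ(−1.54) = 6.2% | 5.3% |

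The last column also counts intervals wholly above 0 that are not wholly above +1. With no effect that adds 2.5% − 0.9% = 1.6 points to the 3.7 points from the lower side. The displaced line favours higher PEEP.

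**5. Duration subgroup: a model with assumed inputs.** The SAP gives no distribution for duration, so every input in this step is an assumption. Let complexity z be standard normal, duration = mean + SD × z, and risk linear in z with slope b. Treatment effect is constant, and one arm's duration is shifted by s minutes. The cut on the z scale is c = (120 − mean)/SD in one arm and c − s/SD in the other. With φ and Φ the standard normal density and distribution function, the mean of z is −φ(c)/Φ(c) below the cut and φ(c)/(1 − Φ(c)) above it. Bias in a stratum is b times the change in that mean.

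- *Worst corner* (mean 150, SD 50, s = +15, b = 8 pp per SD): c moves from −0.6 to −0.9. Below 120 minutes the mean of z goes from −1.215 to −1.446, a bias of 8 × (−0.231) = −1.84 pp. Above, it goes from 0.459 to 0.326, a bias of −1.06 pp. The interaction bias is 1.84 − 1.06 = 0.78 pp.
- *Grid* (mean 120 or 150; SD 50 or 60; shift 5, 10 or 15; slope 4 or 8; 24 scenarios): stratum bias is 0.17 to 1.84 pp for lengthening and 0.18 to 1.73 pp for shortening, in the same direction in both strata. Interaction bias is at most 0.78 and 0.47 pp respectively.
- *Weaker link*: if duration correlates 0.5 with complexity, the bias halves, to 0.08–0.92 pp.
- *Yardstick*: with equal strata the interaction SE is √2 × 2.38 = 3.37 pp, so 0.78 pp is at most about 23% of one SE.

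**6. Cross-check by simulation under different assumptions.** Incidence 23% in both arms, no true effect, mean 120, SD 40, correlation 0.5 between duration and a latent risk factor.

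| Shift in duration | Below 120 min | 120 min or more |
|---|---|---|
| none | +0.1 pp | −0.1 pp |
| +10 min | −0.9 pp | −1.2 pp |
| −10 min | +0.9 pp | +1.4 pp |
| +20 min | −1.9 pp | −2.1 pp |

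The overall difference stays at 0 throughout.

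**The case against.** **On duration.** The bias needs allocation to change duration, and the SAP gives no evidence of that. The test it prescribes is the interaction, which barely moves: the median over the lengthening grid is 0.11 pp against an SE of 3.37 pp. The median stratum bias is 0.57 pp, about a quarter of the stratum SE, and 1.84 pp is one extreme corner. Proposed Table 2 already shows duration by arm, so a shift would be visible, and the SAP openly declares the subgroup as added. Placement in an intraoperative shell is weak evidence, because patient positioning is listed there too.

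Most of this stands, and it limits the weight of the point. The calculations illustrate a mechanism; they do not measure a bias in this trial. But the forest plot also shows the stratum estimates, which are the quantities exposed, and a reader of that figure is not told that this split differs in kind. Nor does the point rest on shell placement alone: with randomisation before surgery, the actual duration cannot be known at allocation, and the SAP names no planned duration.

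**On the line.** It may well be left over from the risk ratio of the original plan. It alters no estimate or p value, and on a proportion axis it would be obviously wrong. That is fair, but the figure description is current text for the main paper. On a percentage-point axis the error is small enough to go unnoticed.

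**Conclusion.** Both parts hold. The reference line is a certain error of display: 1 is not the null on the scale that the same figure specifies. Its size (21% of the half-width in a half-size subgroup, misreading in 13% of rows at the planned effect and 5% at no effect) assumes a percentage-point axis and a reader who takes the solid line as no effect.

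The duration subgroup is a real but conditional flaw. That the split uses the duration actually observed is inferred from the unqualified wording, the time of randomisation and the intraoperative shell; the SAP offers no other variable. Any bias depends on allocation changing duration and on duration being related to risk. It is zero without the former, and of the order of 0.2 to 1.8 pp per stratum under the grid's assumptions. The simulation's 20-minute shift gives up to 2.1 pp. Neither part touches the primary test or the sample size. Both should be corrected before the analysis.

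**What to change.** 1. In the Figure 2 entry of Table 3, place the solid line at 0. The dashed line at the overall effect can stay.
2. Take observed one-lung ventilation duration out of the predefined subgroups, or keep it only as an exploratory analysis labelled post-randomisation, with duration by arm reported beside it. Proposed Table 2 already provides that comparison. Relabelling is enough if the stratification is of clinical interest.
3. Use a pre-randomisation substitute only if one was recorded; the SAP's shells list no planned duration.

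The cost is SAP wording only, with no new data. One stratification is dropped or presented as exploratory.

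### The subgroup by duration of one-lung ventilation is observed only after the randomised strategy has been applied, yet it is presented like the baseline subgroups

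*SAP*

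**What the plan says.** Under Randomization and blinding: "One local investigator randomizes the patients immediately before surgery". The compared strategies are intraoperative.

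Under Subgroup analysis, six subgroups are called predefined. The sixth is "duration of one-lung ventilation < 120 versus ≥ 120 minutes". Nothing in the text says expected or planned duration. Heterogeneity is tested by "use of treatment-by-subgroup term added to the primary model". The list of proposed tables and figures (Table 3) describes Figure 2 of the main paper for all subgroups alike: "A forest plot showing the absolute difference and two-sided 95% confidence intervals with p value for interaction".

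The section on modifications from the original analysis plan records the change: "Added two additional subgroups: body mass index and duration of one-lung ventilation". The SAP was closed in January 2024.

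In the proposed inserts, "Duration of one lung ventilation, min" stands in Table 2, Ventilation and Intraoperative Characteristics, with columns for absolute difference and p value by arm. It is not in the baseline table.

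For surgical approach, the subgroup is "type of surgery (non-thoracoscopic versus thoracoscopic", with two levels. The baseline insert has three rows, the third being "Converted from thoracoscopic to open".

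**The concern.** A subgroup effect has the protection of randomisation when membership is fixed before treatment can influence it. Baseline SpO₂, COPD and body mass index meet that condition. Actual duration of one-lung ventilation does not, because it accrues while the assigned strategy is running. If the strategy makes some patients cross 120 minutes in one arm only, the two arms within a stratum hold different kinds of patients, and a difference in complications can appear although no patient's risk was changed.

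Some influence on duration is possible: only one arm includes recruitment manoeuvres, and hypoxaemia and hypercapnia rescue are counted among the intraoperative complications. The SAP reports no such influence.

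At stake is a row in a main-paper figure that readers may take as showing whether the effect depends on exposure time. The row would sit beside properly randomised comparisons with nothing to mark the difference.

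**Working it through.** **Order of events.** Randomisation comes first (immediately before surgery), then the assigned strategy during surgery, and only then is the duration known. The SAP's own tables agree, since duration is an intraoperative variable compared between arms.

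**Inputs.** From the SAP: 23% complications in the lower-PEEP group, 17.25% in the higher-PEEP group (design effect 5.75 points), N = 2259 before dropout. As a check on N, 2259 / 0.95 = 2378, the planned enrolment. The subgroup analysis has no stated figure of its own to reproduce. Everything about how duration relates to risk, or to PEEP, is assumed below. In every scenario PEEP changes no patient's risk, so the true difference is 0 in each stratum.

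**A. Uniform prolongation.** Assumed: logit(risk) = −1.45 + 0.6u and log(duration) = log 110 + 0.35u + 0.3e, with u and e independent standard normal. Overall risk is then about 21%. In the lower-PEEP arm it is about 16% below 120 minutes and 27% at or above. Duration in the higher-PEEP arm is multiplied by 1.05, 1.10 or 1.15. Rejection rates are at two-sided 0.05 with N = 2259.

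| Prolongation | <120 min | ≥120 min | False interaction | Interaction rejected |
|---|---|---|---|---|
| 5% | −0.4 | −0.6 | 0.2 | 5.0% |
| 10% | −0.8 | −1.1 | 0.3 | 5.1% |
| 15% | −1.1 | −1.6 | 0.5 | 5.2% |

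Differences are in percentage points (interaction in absolute size). Both strata falsely favour higher PEEP, so the interaction largely cancels. The largest value is 1.6 / 5.75 = 28% of the design effect. The tests within strata reject about 5.4–5.5%, 6.6–6.9% and 8.4–9.2% of the time across the three rows.

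**B. Selective movement.** Assumed: half the patients below 120 minutes, with risks of 18% and 28% (overall 0.5 × 18 + 0.5 × 28 = 23%). A share m of the higher-PEEP arm, with risk r, moves from the short to the long stratum. The risks in that arm become

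- short: (0.5 × 0.18 − m r) / (0.5 − m)
- long: (0.5 × 0.28 + m r) / (0.5 + m)

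For m = 5% and r = 40%:

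- short: (0.090 − 0.020) / 0.45 = 15.6%, a difference of −2.4 points
- long: (0.140 + 0.020) / 0.55 = 29.1%, a difference of +1.1 points
- false interaction: 3.5 points, standard error about 3.5 points, rejected 17% of the time instead of 5%

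| m | r | <120 min | ≥120 min | False interaction | Rejected |
|---|---|---|---|---|---|
| 0 | any | 0 | 0 | 0 | 5.0% |
| 2% | 40% | −0.9 | +0.5 | 1.4 | 6.8% |
| 5% | 18% | 0 | −0.9 | 0.9 | 5.8% |
| 5% | 28% | −1.1 | 0 | 1.1 | 6.2% |
| 5% | 40% | −2.4 | +1.1 | 3.5 | 17% |
| 10% | 40% | −5.5 | +2.0 | 7.5 | 59% |

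The bias therefore depends on how many patients cross the cut and on how far their risk differs from that of the stratum they leave or join.

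**The case against.** The strongest reply is that the planned test is the interaction, and under uniform prolongation it keeps its level almost exactly. That stands. It also means that a reader who infers that this subgroup will produce false effect modification, or that it can say nothing about exposure time, goes beyond the evidence. Material error in the interaction needs selective movement of 5–10% of one arm at high risk, and nothing in the SAP supports those figures. The within-stratum estimates are nevertheless shown in the figure, and they carry the bias in either scenario.

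A second reply is that the planned comparison of duration between arms lets a reader see whether the strategy moved it. This helps, but only in part. The comparison is in another table, it is summarised by medians, and a median can stay still while a few per cent of patients cross 120 minutes.

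A third reply is that subgroup analyses are secondary and the subgroup was specified before the final analysis. Both are true. Specifying it in advance guards against selection after seeing results, but does not turn a variable measured after randomisation into a baseline one.

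A reader might also infer that surgical approach has the same defect because conversions occur during surgery. The SAP does not support this. It does not say that the subgroup uses the performed approach or that converted patients join the non-thoracoscopic stratum, and the three baseline rows allow the planned approach to be rebuilt (thoracoscopic plus converted versus open). Only the mapping of conversions is unstated.

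**Conclusion.** The point holds for duration of one-lung ventilation. It is a post-randomisation variable by the SAP's own classification, and presenting it on equal terms with baseline subgroups, without a caveat, is a poor choice. Whether this causes bias, and how much, cannot be settled from the documents. The range runs from none, if the strategy does not alter duration, through about 1 point with the interaction rejected about 6–7% of the time under mild movement, to 7.5 points and 59% in the most extreme scenario examined. All of these rest on assumed links between duration, risk and PEEP. The primary analysis is untouched. The change is worth making because it costs little and the influence on duration cannot be known in advance. For surgical approach, only a one-line clarification is needed.

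**What to change.** Take duration of one-lung ventilation out of the main subgroup forest plot. Show it in a separate supplementary panel labelled post-randomisation and exploratory, with no claim of effect modification, next to the by-arm duration already planned in the intraoperative table. Adding the share of each arm at or above 120 minutes would make movement across the cut visible. Alternatively, replace it with a variable known before randomisation, if one is collected. The insert lists type of resection among intraoperative characteristics, so a planned version should not be assumed to exist.

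As a minor clarification, state that type of surgery means the planned approach, with conversions counted as thoracoscopic.

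The cost is SAP wording and one figure. The downside is that one subgroup becomes descriptive only.

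### The exploratory count analysis leaves out center, by which randomization is stratified, so its test is mildly conservative

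*SAP*

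**What the plan says.** Randomization and blinding: allocation is 1:1 in "permuted blocks of random size of four, six, and eight patients, and stratified per center".

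Primary outcome and Secondary outcomes: the models for the primary and the binary secondary outcomes are fitted "with sites included as random effects to account for the clustering effect". Continuous outcomes use a "mixed-effect median regression with sites also including as clustering effect". The 90-day mortality model is a Cox model "without adjustment for covariates and including sites as frailty".

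Subgroup analysis: heterogeneity is tested by a "treatment-by-subgroup term added to the primary model", so these models inherit the site effect.

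Other exploratory analyses: for the number of positive components, "The groups will be compared on the count using a Wilcoxon rank sum test", and a cumulative logistic model supplies the odds ratio and its 95% interval. The footnote to the eTable 11 template repeats this pairing: the interval from a proportional odds model, the p value from the Wilcoxon test. Site is named in neither place. The GEE models are described only as having several outcomes per subject, again without site.

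Table 3 and the eTable 11 template head these results "Sensitivity Analyses for the Primary Outcome". No general statement in the SAP extends site adjustment to them. The table of modifications moves the primary and binary secondary models to random site effects and lists no matching change for the count analysis.

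**The concern.** When arms are balanced within each center by blocking, differences in risk between centers hardly affect the treatment contrast. A rank test that ignores center still includes those differences in its variance, so its Z statistic varies less than a standard normal under the null. The test then rejects too rarely and loses some power.

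The SAP recognizes center in every model for the primary, secondary, survival and subgroup results, but not in the count analysis that is meant to show whether the handling of the composite matters. At stake are the calibration and power of one supportive analysis.

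**Working it through.** **Inputs from the SAP.** Blocks of 4, 6 and 8 within center; 1:1 allocation; PPC incidence 23% and 17.25%; two-sided 5%; 90% power; N = 2259 before dropouts (Table 2).

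**Assumptions (not in the SAP).** Number and sizes of centers; between-center variation; distribution of the count, taken as P(≥1) = 23%, P(≥2) = 8%, P(≥3) = 3%.

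**The plan's own figure.** A fixed design needs 1020 per arm, 2040 in total. The five-look design with gamma −4 and −2 has an inflation factor of 1.101, giving 2040 × 1.1013 = 2247 against the stated 2259. With 5% dropout, 2259 / 0.95 = 2378, as stated. None of this depends on the count analysis.

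**Mechanism.** With midranks R, the plain test is

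Z = [W − n₁(N+1)/2] / √[(n₁n₀/N) · S²_R],

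where W is the rank sum in one arm and S²_R is the total variance of the midranks. With arms balanced within center, the true variance of W depends only on the within-center part of S²_R. So Var(Z) ≈ 1 − ρ, where ρ is the between-center share of the rank variance. The actual level at a nominal 5% is 2Φ(−1.96 / SD(Z)).

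**Simulation 1.** N = 2258, 50 unequal centers, the SAP's block sizes, 2000 null trials and 600 trials under the alternative per setting. The alternative odds ratio is (0.1725/0.8275)/(0.23/0.77) = 0.70. The comparator is a center-stratified rank test (overall ranks, within-center variance). The center SD on the log-odds scale is √[ICC/(1−ICC) · π²/3].

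| ICC | Center SD | Null SD of Z, plain / stratified | Level, plain / stratified | Power, plain / stratified |
|---|---|---|---|---|
| 0.02 | 0.26 | 0.99 / 0.99 | 5.1% / 5.2% | 92.2% / 92.2% |
| 0.05 | 0.42 | 0.98 / 0.99 | 4.3% / 4.4% | 91.5% / 91.8% |
| 0.10 | 0.60 | 0.98 / 1.02 | 5.0% / 5.7% | 90.7% / 91.5% |
| 0.20 | 0.91 | 0.92 / 0.98 | 3.2% / 4.4% | 88.2% / 89.0% |

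The Monte Carlo standard error is √(0.05 × 0.95/2000) = 0.5 points for a level and about 1/√(2 × 2000) = 0.016 for an SD. Only the last row departs clearly from nominal. There the unrounded SD is 0.915, so ρ ≈ 1 − 0.915² = 0.16, and the formula gives 2Φ(−1.96/0.915) = 3.2%, as simulated.

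**Simulation 2.** 60 unequal centers, the same block sizes, an ordinal count, and van Elteren as comparator. At center SD 0.3 to 0.5 there was no visible effect. At 0.8 to 1.0 the null SD of the plain Z was about 0.93, the level about 3% against 4 to 5% for van Elteren, and power about 2 points lower. By the formula, 2Φ(−1.96/0.93) = 3.5%. In the same settings the unadjusted log-odds-ratio standard error was about 4 to 7% too large for the marginal odds ratio that it estimates.

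**The case against.** The analyses sit under an exploratory heading, and no success rule, alpha or stopping decision depends on them. The error is only in the conservative direction, and at modest between-center variation it cannot be told from simulation noise. All of this stands and sets the weight of the point.

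Four stronger readings are tempting, and the documents do not support them.

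- *That the intervals are simply too wide and adjustment would narrow them.* The Wilcoxon test yields only a p value. The interval comes from the cumulative logistic model, and conditioning an odds ratio on site changes the estimand. In a check on the binary composite (70 assumed centers, 100 trials per setting, site as fixed effects), the adjusted log-odds-ratio standard error was 3%, 7% and 9% larger at center SD 0.5, 0.8 and 1.0. The mean Z (in absolute value) still rose, from 3.11 to 3.21, 3.16 to 3.35 and 2.91 to 3.16.
- *That a discrepancy with the primary result could be put down to site.* The primary analysis is a risk difference on a binary outcome. The count analysis is an odds ratio on an ordinal one. Scale and outcome already differ, so adding site would not by itself make the two comparable.
- *That the GEE models exclude center.* The SAP is silent there. Many site terms with rare components may also fail to converge.
- *That false-positive risk rises.* It does not; the plain test showed no excess of rejections in any setting.

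What survives is that the count test is specified in full, twice, without the randomization stratum that the plan uses elsewhere, and that a better-matched test is readily available.

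**Conclusion.** The point holds as a minor one. The count analysis should respect the center stratification. Over assumed center SDs of 0.3 to 1.0 on the log-odds scale, omitting center gives a null SD of Z of about 1.0 to 0.93 and costs 0 to about 2 points of power; the effect is clear only from about 0.8 upward. The size rests on assumed center numbers, between-center variation and count distribution. The direction follows from the blocking. The primary analysis, its conclusion and the sample size are untouched.

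**What to change.** In Other exploratory analyses and in the eTable 11 footnote, replace the plain Wilcoxon test with the van Elteren test stratified by site, with a rule fixed in advance for pooling very small sites. Add a random site intercept to the cumulative logistic model and state that its odds ratio is then conditional on site.

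Optionally, state how the GEE models treat center: include it only in a form that remains estimable with rare components, or say that these models are deliberately unadjusted.

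The cost is a few sentences and standard code. No new data are needed.
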